1.2 What is/are the principal research question(s) to be addressed?

The primary aims are to:

1. Determine the efficacy of two online (O) versions of empirically-supported psychotherapies for treating FSD: *Cognitive-Behavioural Therapy (CBT-O)* and *Mindfulness-Based Therapy (MBT-O)* compared to a wait list. Primary endpoints are changes in sex-related distress and sexual desire from pre- to post-treatment and persistence of improvement at 6-month follow-up.
2. Compare CBT-O with MBT-O for treating FSD, measuring pre- to post-treatment change in sex-related distress and sexual desire and sustainment of improvement at 6-month follow-up.
3. Evaluate participant satisfaction and compliance using these online programs with weekly individualized support from a non-expert navigator.

We ([name], [name], [name]) are experts in CBT and/or MBT for face-to-face and web-based treatment of sexual difficulties.⁹⁻¹⁷ We have worked with [name], a professional graphic and digital designer, to develop **eSense**: an online platform to deliver CBT and MBT treatments adapted for web-based, self-directed therapy. We believe that eSense is efficacious, has the potential to improve accessibility and affordability of evidence-based treatment, and has long-term potential to be commercialized. I ([name]) am lead creator and evaluator of the most widely-validated MBT intervention for FSD,¹⁸ which can be readily adapted for online use. To our knowledge, there is no equivalent CBT intervention for FSD that is comprehensive and available. Therefore, much of our work to date has focused on creation and testing of the CBT “arm” of eSense.

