1.4 How will the results of this trial be used?

The study will yield effect sizes for primary endpoints of sexual desire and sexual distress that we will use in a subsequent larger RCT application. This study will advance health-related knowledge by providing new data on the relative efficacy of online CBT and MBT for FSD and health outcomes by having the potential to increase access to effective treatment for women living in rural and remote areas as well as those who experience other barriers in accessing face-to-face care. Thus, this research program has a high likelihood of filling a major gap in healthcare of women and eSense has significant potential for commercialization. UBC's University-Industry Liaison Office has committed to supporting this project through to commercialization (see Letter of Support, **Appendix**).

I ([name]) have expertise with Knowledge Translation (KT) methods. I have held KT grants from CIHR (DGE129657) and MSFHR (#17403, 2017-18; #18793, 2019-20) for social media campaigns, and received UBC's 2020 President's Award for Public Education through Media for KT output. As Executive Director, Women's Health Research Institute, I supervise skilled research managers who have advanced training in KT and implementation science. For this project, we will use integrated and end-of-grant KT, and have an established patient advisory group with whom we meet twice/year. We plan to publish the pilot RCT findings (given dearth of relevant publications). The findings will also be disseminated through traditional conference and rounds presentations, an infographic video, and a public forum for women, co-designed with our patient advisory group. The forum information will be used to design our future RCT.

1.5 Are there any risks to the safety of participants involved in the trial?

Owing to the sensitive nature of sexual content in the intervention, participants will have the option to contact the coordinator (supervised by licensed psychologists [name] and [name]) for guidance on sexually-based concerns. After data have been cleaned and checked (Q2 Y3), participants will be provided unrestricted access to content in both intervention arms, which they can use at their leisure. This adds no cost to our budget. Privacy will be maintained and absolutely no identifying information will be linked to data.

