2.3 What are the proposed practical arrangements for allocating participants to trial groups?

Randomization: Participants will be randomized to one of 3 arms in a 1:1:1 sequence (CBT-O: MBT-O: wait-list control) using the Blockrand package in R, with random block sizes. Those in the wait-list group will complete two online questionnaire/assessment batteries before being randomized to one of the active treatment groups. As indicated in the Figure (next page), the n=30 women randomized to wait-list will be enrolled in a treatment arm after the wait-list period is complete. No stratification will be used in this pilot study.

Waitlist control: Face-to-face FSD intervention studies consistently find no passage-of-time-only changes in participants assigned to waitlist control groups^{11,58}. As such, to maximize the opportunity to estimate treatment effects while minimizing costs of this pilot study, we propose a **modified waitlist control group**. At study onset, participants will be assigned randomly to the waitlist group; at the end of the waiting period, they will be randomized into 1 of the 2 treatment groups. They will receive 2 assessments: at waiting period start and after randomization to treatment (Fig 1, next page). Pre- and post-waiting period assessments will be compared to check for a passage-of-time effects. Starting at post-waiting period assessment, their data will be combined with the rest of the participants for treatment evaluation analyses.

What are the proposed methods for protecting against sources of bias?

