2.15 How many centres will be involved?

Though the team of investigators come from 4 different institutions, all study activities will take place in the NPA's laboratory at UBC.

2.16–2.18 What is the proposed type of analyses? What is the proposed frequency of analyses?

Statistical analysis: Effect of treatment will be determined by analyzing baseline (pre) to post-treatment changes after CBT-O and MBT-O on sexual distress (FSDS-R) and sexual desire (SIDI) scores. Sustainability of treatment effects will be evaluated by adding the follow-up measurement point to the model. Both analyses will be conducted using a multilevel mixed effect model analysis with one within-subject factor of time (treatment) based on 2 or 3 measurement points (baseline and post-treatment in the first analysis; plus 6-month follow-up for the second analysis) and one between-subject factor (CBT-O vs MBT-O) as well as their interaction. Interactions will test for differences in the amount of change due to treatment between arms. We will calculate effect sizes and confidence intervals (CI) and use descriptive statistics for measures of treatment satisfaction and compliance. These values will be compared between treatment arms. Treatment length will vary from 8 to 12 wks, so individual length of treatment will be added as a control variable in all initial models. Notable differences will guide changes that may increase satisfaction/compliance before we conduct a larger RCT following completion of the current pilot study.

Missing data: Mixed-effects modelling allows for missing data and uses all available data for estimating model parameters. Incomplete outcome data can restrict the sample size available for tests of interactions. We will impute missing outcome data using multiple imputation techniques. We will run a sensitivity analysis to compare analysis that uses multiply-imputed data to analysis that includes missing data.

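### The CBT-O versus MBT-O comparison (primary aim 2) is valid as planned, but less precise than a model that uses the baseline already collected

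*Combined protocol and SAP*

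**What the plan says.** Primary aim 2 in section 1.2 is stated as "Compare CBT-O with MBT-O for treating FSD, measuring pre- to post-treatment change in sex-related distress and sexual desire", with persistence at 6 months. Section 2.16–2.18 fits a multilevel mixed model to FSDS-R and SIDI. Baseline is one of the two or three levels of time, arm (CBT-O or MBT-O) is the between-subject factor, and their interaction is included. On the arm comparison it says: "Interactions will test for differences in the amount of change due to treatment between arms". For 6 months: "Sustainability of treatment effects will be evaluated by adding the follow-up measurement point to the model". On incomplete data: "Mixed-effects modelling allows for missing data and uses all available data for estimating model parameters"; multiple imputation is also planned. The covariate named in that section is individual length of treatment, to be included in all initial models. The bias-protection text after section 2.3 and section 2.6–2.7 add that navigator effects will be controlled for. Nowhere is the baseline score named as a covariate, or the baseline mean set equal across arms.

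Wait-list women join this comparison after waiting (section 2.3): "Starting at post-waiting period assessment, their data will be combined with the rest of the participants for treatment evaluation analyses". Section 2.3 puts that second assessment before their randomisation to a treatment: "Those in the wait-list group will complete two online questionnaire/assessment batteries before being randomized to one of the active treatment groups". It also puts it after: "They will receive 2 assessments: at waiting period start and after randomization to treatment". The assessment-points paragraph of section 2.6–2.7 contains both orders too.

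Section 1.4 explains the use of the results: "The study will yield effect sizes for primary endpoints of sexual desire and sexual distress", for a later, larger trial application.

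**The concern.** An arm main effect plus an interaction gives each arm its own freely estimated baseline mean. In a randomised comparison the two true baseline means are equal, so chance imbalance at baseline is carried into the estimated difference in change. A model that uses this equality estimates the same arm difference with less noise. At stake is the width of the interval for a primary aim, in a pilot whose stated product is effect sizes for a later trial.

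The gain relies on baseline being measured before randomisation. For the wait-list third of the sample (43 of 129) the text leaves this open. If that assessment follows randomisation, those women might know their arm when giving their baseline, which would affect the planned change analysis as well.

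**Working it through.** **Plan's own figure.** Section 2.10 aims for 30 per arm after 30% attrition: 30/0.70 = 42.9, so 43 per arm and 129 in total. This reproduces. The documents give no precision figure for the interaction.

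**Inputs.** Assuming the second randomisation is 1:1 (ratio not stated), each treatment arm has N = 43 + 43/2 = 64.5 women with a baseline and n = 30 + 15 = 45 with post-treatment data. Let baseline SD = 1, k = post/baseline SD ratio and rho = baseline–post correlation. Neither k nor rho is in the documents. Section 2.19 gives t(57) = 6.43 and t(58) = 8.13; 6.43/√58 = 0.844 and 8.13/√59 = 1.058. These match the stated d of 0.85 and 1.06, so those effect sizes are scaled by the SD of change and do not reveal rho. I therefore take rho 0.3–0.7 and k 0.8–1.25.

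**Formulas** (variance of the post-treatment arm contrast, treatment length omitted from both models):

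- Free baseline means, all available data: V1 = 2[k²(1−rho²)/n + (1−rho·k)²/N]
- Common baseline mean or baseline-adjusted: V2 = 2k²(1−rho²)/n
- Gain = 1 − V2/V1

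**Example**, k = 1 and rho = 0.5: V1 = 2[0.75/45 + 0.25/64.5] = 0.0411; V2 = 2(0.75/45) = 0.0333; gain 18.9%.

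Reduction in variance at 30% attrition:

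| k | rho 0.3 | rho 0.5 | rho 0.7 |
|---|---|---|---|
| 0.8 | 40.9% | 34.4% | 29.3% |
| 1 | 27.3% | 18.9% | 11.0% |
| 1.25 | 16.1% | 7.7% | 1.3% |

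A simulation (20,000 trials per scenario, 64 per arm, 45 observed) gave 26.5%, 18.7% and 10.1% at k = 1, and 40.4% and 0.5% at the two extremes. Both estimators were unbiased.

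**Sensitivity to attrition and numbers.** At the 54% attrition quoted in section 2.13–2.14 (n = 29.7), the k = 1 row becomes 19.9%, 13.3% and 7.5%. Section 2.3 speaks of 30 wait-list women moving to treatment. If N = 43 + 15 = 58 and n = 45, the gain at k = 1, rho = 0.5 is 0.25/(0.75 × 58/45 + 0.25) = 20.5%, so the conclusion is unchanged.

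**Six months.** Gains equal those at post-treatment if the correlations are the same and nobody else is lost. If attrition reaches 54% by then and the baseline–6-month correlation is 0.8·rho, they are 22.4%, 17.2% and 12.5% at k = 1.

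**In scale points.** Section 2.19 implies an SD of change of 9.4/0.844 = 11.1 (FSDS-R) and 11.0/1.058 = 10.4 (SIDI), from face-to-face treatment. At rho = 0.5 and 30% attrition the 95% CI half-widths (1.96 × baseline SD × √V, with baseline SD = SD of change/√(1 + k² − 2·rho·k)) are:

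| k | FSDS-R | SIDI |
|---|---|---|
| 0.8 | 4.29 to 3.48 | 4.01 to 3.25 |
| 1 | 4.42 to 3.98 | 4.13 to 3.72 |
| 1.25 | 4.53 to 4.35 | 4.22 to 4.06 |

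**Treatment length.** Length is known only after randomisation. As a main effect it cancels from the planned interaction with complete data, but not from a baseline-adjusted contrast. Illustration, on assumed values: rho = 0.5, length differs by 0.5 SD between arms and correlates 0.4 with a woman's underlying level, and there is no true arm difference. The correlation of length with each score is 0.4 × √0.5 = 0.283. The coefficient of length given baseline is (0.283 − 0.283 × 0.5)/(1 − 0.283²) = 0.154. The arm estimate is then shifted by −0.5 × 0.154 = −0.077 SD. Simulation gave −0.078 for baseline adjustment plus length, −0.069 for a common baseline mean plus length, and essentially zero for the planned interaction or a common baseline mean without length.

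**The case against.** The strongest case for leaving the plan alone is that nothing in it is wrong. Aim 2 is framed as a comparison of change, the interaction estimates exactly that, and this is a pilot. That stands, and it is why this is an improvement rather than a correction. The common-baseline model targets the same arm difference and still yields the pre-post change, so nothing is given up.

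A second objection is that the size rests on unknown inputs and runs from negligible to large. That also stands. Near rho = 0.7 with k = 1.25 there is almost nothing to gain.

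A third is that the calculation leaves out treatment length, so it is not a figure for the exact planned model. This is correct. If dropouts have no recorded length and a standard fit discards them, both models use the same women and the equal-SD gain is (1−rho)/2, or 35%, 25% and 15%. The same objection exposes a real hazard: switching to baseline adjustment while keeping length in the model could make a valid estimate biased. The recommendation has to deal with that.

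Multiple imputation under a similar model would not close the gap, since separate baseline means would remain.

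On timing, sections 2.3 and 2.6–2.7 each include an explicit order with questionnaires first, and the referenced figure is not shown. The contrary wording may be a slip, but it needs reconciling.

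**Conclusion.** The point holds as a free improvement. Relative to the all-available-data interaction model without treatment length, using the collected baseline would lower the variance of the post-treatment arm contrast by about 11–27% with equal SDs, or about 1–41% across SD ratios of 1.25 to 0.8. This assumes rho 0.3–0.7, 30% attrition and a 1:1 second randomisation. At equal SDs it is worth about 12–38% more participants (1/0.89 to 1/0.727). The pooled pre-post change gains essentially nothing.

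A reader might infer that the planned interaction is biased or invalid. The documents do not support that: it is an unbiased estimate of the arm difference in change, under the usual missing-at-random condition. A reader might also infer that wait-list women will know their treatment when they give their baseline. That is only a possibility. The text contradicts itself on the order, and no section supplied says when allocation is disclosed.

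**What to change.** 1. Reconcile sections 2.3 and 2.6–2.7 so that the wait-list assessment used as baseline is completed before randomisation to CBT-O or MBT-O. This is needed under the planned model too.
2. For the arm contrast, use a longitudinal mixed model with unstructured covariance and a baseline mean common to both arms within randomisation stage (at entry, or after the wait list). Alternatively, adjust for the pre-randomisation score; that route needs a separate model for the pre-post change.
3. Leave individual treatment length and other post-randomisation covariates, such as the navigator measures collected at post-treatment, out of this contrast. Equal baseline means do not hold conditional on them. Models that include them can be secondary.
4. Report the arm difference with its 95% CI at post-treatment and at 6 months, and keep the planned interaction as a sensitivity analysis.

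Substituting the score from the start of the waiting period is not a good way around step 1, because it can lose precision.

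The cost is wording in the analysis plan and in the two sections on timing, plus a small amount of analysis work. No new data, visits or software are needed.

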During the study, women must agree not to change medications known to have sexual side-effects unless mandated by their physician (medication use data will be collected at each assessment point). Participants will be encouraged to limit/eliminate internet use as a source of additional information about sexual dysfunction during the trial (and asked about this at post-treatment). We have found this request feasible in past^{9,87} research. Every 3 months, we will analyze recruitment for group differences in ethno-cultural categories and sexual orientation, and adjust recruitment efforts to ensure that our sample reflects cultural and sexual diversity of the population of Canada and the United States, and is balanced across arms. The coordinator gathering data will not be involved in administering or navigating treatment. To minimize inter-navigator variation, navigators will receive training from [name], CoA [name], and [name]. Specifically, each navigator will receive a reading list of readings relevant to treatment of women's sexual concerns. Navigator-related measures will be evaluated for potential effects on outcomes and controlled for.

[figure not shown]
Navigator related measures include:

1. Empathy subscale of the Barrett-Lennard Relationship Inventory, a valid measure of perceived provider empathy that predicts outcomes in CBT (this was already uploaded in Rise).
2. Perceived navigator effectiveness with the Working Alliance Inventory, Short Form (this was already uploaded in Rise).
3. In addition, each navigator will keep track of the number of minutes spent with each participant over the course of the 8 modules, and this number will also be used as a moderator.

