2° outcomes: Treatment satisfaction will be assessed with (i) two face-valid single item measures measured on through the eSense platform at the beginning of modules 2-8 and measures via Qualtrics a week after completing module 8 asking participants to rate helpfulness of content covered in the previous module, and ease of reading the content (1-10 scale); Research suggests a cut-off of 6.5/10 on these measures to indicate acceptable utility and clarity of content⁹⁴; (ii) qualitative feedback about website and homework assignments collected by treatment navigators; (iii) adapted Erectile Dysfunction Inventory of Treatment Satisfaction,⁹⁵ a widely used scale measuring satisfaction after treatment for erectile dysfunction. Perceived relationship with navigators is assessed at post-treatment with two measures: (i) Empathy subscale of the Barrett-Lennard Relationship Inventory,⁹⁶ a valid measure of perceived provider empathy that predicts outcomes in CBT⁹⁷; (ii) perceived navigator effectiveness with the Working Alliance Inventory, Short Form.⁹⁸ Treatment compliance will be measured by: (i) recording number of weeks and treatment sections completed⁹⁹; (ii) eSense website engagement and performance by Google analytics (e.g., page views, # visits/sessions, page views/visit, visit duration, unique/returning users); these metrics are recommended by the E-CONSORT guidelines as important for e-health intervention studies. The platform used to house eSense tracks views of a page and completion of the overall program, enhancing and complementing what analytics can provide; (iii) navigators will ask participants to rate homework completion on a Likert scale ranging from “did not attempt” to “successfully completed all assignments” weekly; (iv) having participants complete the Homework Rating Scale-II (HRS-II)¹⁰⁰ at the beginning of modules 2-8 on the eSense platform and then complete it again week via Qualtrics after completing module 8 to provide a comprehensive measure of experience with the homework; (v) measuring navigator adherence to study guidelines by coding a random 20% of Zoom sessions (participants will be informed of these recordings) for adherence (to be done by [name]’s trainee; no funding requested), using a previous adherence scale we have used.^{17,81} Sexual function will be measured using the total score of the Female Sexual Function Index,⁹¹ a validated self-report measure of sexual function.

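### No CBT-O versus MBT-O arm × time model free of post-randomisation covariates is designated primary for FSDS-R and SIDI

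*Combined protocol and SAP*

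**What the plan says.** Section 2.16–2.18 (Statistical analysis) sets out a mixed model for FSDS-R and SIDI with time, arm (CBT-O or MBT-O) and their interaction. The interaction carries the arm comparison: "Interactions will test for differences in the amount of change due to treatment between arms". The same paragraph notes that treatment will last 8 to 12 weeks and concludes that "individual length of treatment will be added as a control variable in all initial models". It also summarises satisfaction and compliance measures and says "These values will be compared between treatment arms".

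The subsection on protecting against bias, which follows section 2.3, says "Navigator-related measures will be evaluated for potential effects on outcomes and controlled for". It names empathy, working alliance and contact time as those measures. On contact time, "each navigator will keep track of the number of minutes spent with each participant over the course of the 8 modules", and that count is to serve as a moderator. Section 2.6–2.7 adds that the impact of navigators will be assessed before the main analyses and then controlled for.

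Section 2.8–2.9 places several of the same quantities under secondary outcomes: "Treatment compliance will be measured by: (i) recording number of weeks and treatment sections completed" and "Perceived relationship with navigators is assessed at post-treatment with two measures".

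The only sensitivity analysis named, in section 2.16–2.18, compares imputed with non-imputed data.

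**The concern.** A variable that arises after randomisation can itself be affected by the arm. If the CBT-O versus MBT-O comparison is adjusted for it, the result need no longer be the effect of allocation. Here the plan treats some quantities as results of treatment and also as controls for the primary outcomes.

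The arm contrast is Aim 2 (section 1.2), and the effect sizes are to be used for a larger trial (sections 1.4 and 2.8–2.9). With no covariate-free model fixed in advance, and no rule for moving from the initial models to a final one, the reported contrast could depend on a modelling choice that the plan leaves open.

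**Working it through.** **1. Timing and roles, set side by side**

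| Variable | When it arises | Listed under outcomes (2.8–2.9) | Role in the models |
|---|---|---|---|
| Treatment length | During treatment, self-paced at 1–2 weeks per module (2.2) | Yes, weeks completed | Control in all initial models (2.16–2.18) |
| Navigator minutes | Accrue over the 8 modules | No | Moderator, and among the measures to be controlled for |
| Empathy and alliance ratings | Post-treatment | Yes | Controlled for |

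None is known at randomisation. No main-effect, by-time or by-arm form is written down for any of them.

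**2. Additive form**

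For woman i with covariate C:

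y = β0 + β1·arm + β2·time + β3·arm×time + γ·C + (woman effect) + error.

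Subtracting baseline from post-treatment gives:

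change = β2 + β3·arm + (difference in errors).

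C cancels, so with complete pre/post data β3 is the difference in mean change whether or not C is in the model.

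- One complete simulated dataset gave arm × time estimates of 0.484 without length and 0.484 with length as a main effect. With length × time the estimate was 0.178.
- With 64 + 65 women, about 30% of post-treatment scores missing and C observed for all (1,500 replicates), the mean difference between the additive and covariate-free estimates lay between −0.0004 and 0.0017 SD.

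**3. Covariate × time form**

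Now change = β2 + β3·arm + δ·C + error. Assumed set-up, with no true arm difference:

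- C = s·arm + a·U + noise.
- Post = r·baseline + b·U + noise.
- U is a shared cause, variances are 1, and r = 0.5.
- There are 45 women per arm, from 129 × 0.7 / 2 = 45.15 (the recruitment target and attrition in section 2.10).

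Within arm, the slope of change on C is a·b, so the bias in β3 is −a·b·s. The values of a, b, s and r are assumptions; the documents give none of them.

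| Arm gap s (SD) | Bias, a = 0.6, b = 0.4 | Type I error | Bias, a = 0.3, b = 0.2 |
|---|---|---|---|
| 0 | 0 | 5.0% | 0 |
| 0.1 | −0.024 | 5.2% | −0.006 |
| 0.3 | −0.072 | 6.4% | −0.018 |
| 0.5 | −0.120 | 8.7% | −0.030 |
| 0.8 | −0.192 | 13.9% | −0.048 |

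Type I errors come from 20,000 replicates. With the weaker loadings they were 5.1–5.4%. With C omitted, absolute bias was at most 0.004 and type I error 4.9–5.4%. The standard error of the contrast was 0.205–0.223 SD.

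**4. Scale in points**

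Section 2.19 gives paired t statistics for face-to-face MBT. The effect sizes follow as t/√n:

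- FSDS-R: 6.43/√58 = 0.844 (stated 0.85).
- SIDI: 8.13/√59 = 1.058 (stated 1.06).

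The implied SDs of change are:

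- FSDS-R: (32.3 − 22.9)/0.844 = 9.4/0.844 = 11.1 points.
- SIDI: (27.9 − 16.9)/1.058 = 11.0/1.058 = 10.4 points.

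At r = 0.5 the variance of change is 2(1 − 0.5) = 1, so the SD of change equals the score SD. A bias of 0.192 SD is then about 2.1 FSDS-R or 2.0 SIDI points. A bias of 0.048 SD is about 0.5 points on either scale, and 0.024 SD is about 0.3.

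**The case against.** The strongest reply is that the plan, read plainly, does no harm. A control variable is normally an additive term, and step 2 shows that such a term leaves the arm × time contrast alone. When the plan means an interaction it says so, as it does for arm and time. The documents also suggest small arm gaps. Both programs have 8 modules (section 2.2), MBT-O follows the CBT-O layout, sessions follow one 15–20 minute outline, and navigator feedback is largely common to both arms (section 2.6–2.7). A bias of 0.072 SD is only about a third of the simulated standard error. Navigator impact could also mean differences between navigators, which is a clustering question. And this is a pilot.

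Most of this stands for treatment length. A reader might infer that the length control biases the primary comparison, but the documents do not support that: nothing says length enters by time. The reply settles less for the navigator measures. Minutes are called a moderator without saying of which effect, and the control for empathy and alliance has no stated form. The plan's reason for the length term is that length varies, yet an additive term cannot adjust change for that, so an analyst pursuing that purpose might choose the other form.

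Two further inferences are tempting and should not be drawn:

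- **Missing ratings.** A reader might infer that women without empathy or alliance ratings would drop out of the model, baseline rows included. But the plan says "We will impute missing outcome data using multiple imputation techniques", and this can cover ratings that it lists as outcomes. Even if the rows were lost, simulated bias was about 0 when dropout worked alike in both arms. It reached 0.07–0.10 SD only when dropout depended on baseline in one arm alone, which nothing in the documents suggests.
- **Navigator-preference code.** A reader might infer that this code (section 2.6–2.7) distorts the contrast. It describes the navigator rather than a woman's response to treatment, and no effect on the contrast has been shown.

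**Conclusion.** The point holds in a limited form. The plan conditions its models for FSDS-R and SIDI on variables that arise after randomisation, lists some of them as outcomes, and designates no arm × time model without them as primary. That much rests on the text alone.

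The harm is conditional. It is nil if the terms are additive and observed for all, or if the arms do not differ on them. In the covariate × time form the illustration gives 0 to about 0.2 SD with type I error of 5–14%, and at most 0.05 SD with weak loadings. All loadings, arm gaps and the correlation are assumed. Stronger inputs give more: loadings of 0.8 and 0.5 with a gap of 1 SD give 0.8 × 0.5 × 1 = 0.40 SD. No document figure supports such inputs, so this is not evidence that the planned analysis is biased to that degree.

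Severity is minor to should-fix. The sample size is not affected.

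**What to change.** In section 2.16–2.18, designate as primary for FSDS-R and SIDI the mixed model already described there. It should be analysed by allocated arm, with arm, time and arm × time, pre-randomisation covariates only, and all women randomised to CBT-O or MBT-O who have any data.

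Move treatment length, navigator minutes, and empathy and alliance ratings to process or moderator analyses labelled exploratory. State there how each term enters. Align the wording on navigator control in the bias-protection subsection and section 2.6–2.7 with this.

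The cost is rewording and slightly more analysis work. No new data are needed, and every process and moderator analysis can still be reported.
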